12. PREVENTIVE MEASURES

Preventive measures include both vaccination and chemoprophylaxis in close contacts of cases. (2,16)

In addition, other effective measures are general recommendations to avoid respiratory transmission such as wash your hands before and after touching a patient, patient isolation,

wear a mask; and inform to the Public Administrations when cases appear in order to put in practice adequate prevention procedures in population at risk. (16)

Chemoprophylaxis

Its main objectives are reducing the transmission of *N. Meningitidis* from sick people or carriers to healthy people and eradicate carriers state in neocolonized who are vulnerable to develop an IMD (those who have been colonized during the last 7 days). ⁽²⁾

The antibiotics for the chemoprophylaxis are:

Drug	Age Group	Doses	Duration
Rifampicin	Children <1 month	5 mg/kg every 12 hours	
Oral	Children > 1 month	10 mg/kg every 12 hours	2 days
administration	Adults	600 mg every 12 hours	
Ceftriaxone	Children < 15 years	125 mg	Single dose
Intramuscular administration	Adults	250 mg	
Ciprofloxacin	Adults*	500 mg	Single dose
Oral administration	*in children can produce arthropathy		

Figure 3. Chemoprophylaxis for IMD from (2)

Vaccinations

Vaccination is a preventive measure that helps to avoid secondary cases of IMD when it is combined with chemoprophylaxis. ⁽⁹⁾ Moreover, it has been recognised as the most effective way of prevent bacterial meningitis in children. ⁽¹⁸⁾

About meningococcal vaccines, in our environment we have an effective conjugated vaccine for prevent IMD due to *N. Meningitidis* serogroup C. This vaccine showed its efficacy during epidemic outbreaks and since year 2000 it is included in our routine vaccination schedule. (2,8,10,24)

It also exists tetravalent conjugated vaccines against serogroups A, C, Y and W135 that are recommended for patients who travel to endemic regions for that serogroups or immigrants who are from those regions.

Nowadays, polysaccharide vaccines are not used today in paediatrics and they have been replaced for conjugated vaccines, which are: more effective, can be administrated in children >2 months and produce a fast and durable T-Dependent immune response. Moreover, this type of vaccine can eradicate carriers, helping to control the disease. (9,16,25)

Recently, a new vaccine has been developed for prevent IMD due to meningococcus serogroup B. Several aspects of that vaccine will be the objective of that protocol.

JUSTIFICATION

Invasive Meningococcal Disease is still today an important infectious disease that causes mortality, morbidity and a big social alarm. Despite of scientific advances, its prompt diagnosis and treatment continue supposing a big challenge for physicians, who must act rapidly, due to the quick onset and course of the disease and the possibility of major sequelae. (2,26)

According to current data about IMD epidemiology, we know that, despite IMD has a tendency to decrease, the main serogroup responsible of IMD cases is meningococcus B in several European countries including Spain. (10,14,15)

Moreover, it is known that an active immunisation through vaccines is the best measure for primary prevention of IMD. (26)

For years, big efforts have been made to develop an effective vaccine against meningococcus B. However, developing that vaccine has been really difficult, because capsular structure of meningococcus B acts as a self-antigen. This fact caused that, conventional conjugated vaccines produce lower immune response thus lower antibodies production and, potentially, autoimmune responses. So, instead of conventional vaccines it was necessary a different type of vaccine. (26)

Finally, on January 2013 a new vaccine called 4CmenB (Bexsero) produced by a new technology, known as reverse vaccinology, was approved for prevent IMD due to meningococcus B.

However, because Bexsero is a new vaccine obtained through a newer technology many aspects about this vaccine are unknown and that fact generates controversy in its use. (14,27,28)

On the one hand, what we know about Bexsero is that the vaccine is immunogenic. That means it generates high antibodies titers with bactericidal activity against antigens included into the vaccine. There are also studies that show the vaccine has been effective for controlling epidemic outbreaks in United States and Quebec. (27,29,30) An important aspect about this information is that it has been obtained in teenagers and adults. (30,31) There are no studies carried out in children.

On the other hand, there are many other things we do not know about Bexsero, such as its real effectiveness in IMD prevention, its safety, its interaction with the other routine

vaccines, its coverage of the meningococcus B strains of our country, the period of time during which the person is protected, if the vaccine is capable of erradicate carriers or if it is recommended in high risk groups of population. (14,27,31)

Hence, given the lack of information about Bexsero the Spanish Vaccinology Association and the Health Ministry (14) as well as work groups for Bexsero's use in special situations (28) have elaborated several documents and recommendations about the use of the vaccine. Together, those entities do not recommend a systematic use of Bexsero.

On the contrary, pediatricians and the Vaccine Advisory Committee of the Spanish Pediatrics Association ⁽¹⁵⁾ advise a routinary use of Bexsero and encourage parents to vaccinate children. In fact, they are asking for introduce Bexsero into the routine vaccination schedule.

Furthermore, other European countries such as Italy (11), France (32) have found different results when they asses the effects of Bexsero in its population.

Recently, United Kingdom has introduced Bexsero as a routine vaccine and, since 2015, they are collecting data about its effectiveness in their population.

In conclusion, given the existing controversies about Bexsero use and the lack of strong evidences about its real efficacy in IMD prevention; further studies are required to really know the effects of that vaccine.

For that reason, the aim of this protocole is designing a study that assesses, mainly, the effectiveness of Bexsero for prevent IMD in children aged among 3 moths and 5 years old, since those are the most affected for this disease and, in addition, there are no studies performed in that age group. Moreover, it will also provide information about its adverse reaction profile.

HYPOTHESIS

PRIMARY

Children under 5 years old who have been vaccinated with Bexsero have lower incidence of invasive meningococcal disease in comparison with unvaccinated children.

SECONDARY

Children under 5 years old vaccinated with Bexsero as well as routinary vaccines show a higher proportion of adverse reactions than those who just receive routinary vaccinations.

OBJECTIVES

MAIN OBJECTIVE

❖ To asses the effectiveness of Bexsero in prevention of invasive meningococcal disease in children aged among 3 months and 5 years old.

SECONDARY OBJECTIVES

❖ To compare the occurrence of adverse reactions among children vaccinated with routinary vaccines and Bexsero versus children vaccinated with routinary vaccines.

METHODOLOGY

STUDY DESIGN

This is an observational prospective cohort study. It will have two groups:

- ❖ Cohort 1: it will include children vaccinated with Bexsero.
- ❖ Cohort 2: it will include children non vaccinated with Bexsero.

The follow-up period will last 5 years, and during that time we will observe how many cases of IMD occur in each cohort to stablish the effectiveness of Bexsero vaccination.

Concurrently, we will collect information about adverse reactions due to vaccination registered in each cohort, in order to compare it.

STUDY POPULATION

The target population of the study are children (boys and girls) aged among 3 months to 5 years old, who are attending to Public Health System and whose data about visits and vaccinations are registered into the SIDIAP.

Inclusion criteria

- Children aged among 3 months and 5 years old.
- Health Centres that participate in the study register patient's information into SIDIAP database.

Exclusion criteria

- Children that are not receiving regularly vaccines.
- Previous antecedent of meningococcal meningitis or sepsis.
- Children with one of the following pathologies: *

Persistent complement deficiencies.

Primary or secondary immunodeficiencies.

Anatomical or functional asplenia.

*The reason why it is necessary to exclude those children is because they have different vaccination regimens from those of the general population.

SAMPLE PROTCOL

Sample selection

The sample will be selected, taking into account the mentioned inclusion and exclusion criteria, from registers contained into SIDIAP database. A non-probabilistic consecutive sampling method is employed in this study.

All children that accomplish previously mentioned criteria will be included.

The enrolment period starts on June 2017 and finishes on June 2018, lasting 1 year.

The desired follow- up for each participant should be 5 years, because this is the period where higher incidence rates occur among paediatric population.

Sample size

The application "GRANMO" has been used to calculate the sample size required. The ARCSINUS approximation has been used.

Accepting an alpha risk of 0.05 and a beta risk of 0.10 in a bilateral contrast, we need 14.108 vaccinated children (cohort 1) and 70.540 unvaccinated children (cohort 2) to detect statistically significant differences, considering an efficacy of Bexsero greater than or equal to 70%.

The incidence of IMD in unvaccinated children has been obtained from official data published by "Red Nacional de Vigilancia epidemiológica (RENAVE)" and is 16 cases /100.000 hab per year.

Dropout rate is estimated as 5%.

STUDY VARIABLES

❖ Independent variable: In this study, independent variable is defined as to have been or not to have been vaccinated with Bexsero.

To classify a child as vaccinated, he must have finished the vaccination regimen according to his age as we can see in the table below adapted from the technical file of Bexsero. Booster doses are not required to consider a child as correctly vaccinated.

Age group	Primary	Dose interval	Booster dose
	immunisation		
From 2 months to	3 doses of 0.5 ml	At least 1 month.	1 dose between 12
5 months	each one, starting		and 15 months.
	the first dose at 2		Never after 24
	months or later.		months.
From 6 months to	2 doses of 0.5 ml	At least 2 months.	1 dose during the
11 months	each one.		second year of life
			with a minimum
			dose interval of 2
			months since the
			primary
			immunisation.
From 11 months to	2 doses of 0.5 ml	At least 2 months.	1 dose with a dose
23 months	each one.		interval from 12 to
			23 months since the

			primary immunisation.
From 2 years to 10 years	2 doses of 0.5 ml each one.	At least 2 months.	Not established.
11 years or more	2 doses of 0.5 ml each one.	At least 1 month.	Not established.

Vaccination's state will be collected checking the code corresponding to Bexsero: **P00157**.

❖ Outcome variable: In that case, outcome variable for the primary objective is the number of cases of IMD. As it has been said in the introduction we mainly consider IMD as:

Meningitis: it is defined as an inflammatory process of the leptomeningeal membranes who overcoat the CNS.

Information about diagnosis of meningococcal meningitis is codified in hospital registers as **036.0**.

Sepsis: it is defined by the presence of systemic inflammatory response syndrome due to an infection (suspected or confirmed). That syndrome is characterised by the presence of 2 of the following:

- Axillary temperature >38°C or <35,5°C. *
- Tachycardia: cardiac frequency >2 Standard Deviations according to the age of the patient without medication or external or painful stimuli.
- Tachypnea: respiratory frequency > 2 Standard Deviations according to the age of the patient.
- White cell count elevated or diminished for the age of the patient or >10% of immature neutrophils. *

Information about diagnosis of sepsis is codified in hospital registers as **036.2** (meningococcal sepsis) and **036.3** (Sd. Waterhouse-Friedrichsen).

Finally, the outcome variable for the secondary objective are adverse reactions due to vaccination.

^{*} Criteria must be present.

Adverse reaction: it is defined as a harmful and undesirable reaction which is produced with normal doses used in humans for prevent, diagnose or treat a disease.

We consider adverse reactions all reactions, local or systemic, caused by vaccinations:

Local adverse reaction: local pain, cutaneous erythema, swelling.

Systemic adverse reaction: Fever >38°C, irritability, bad general condition.

Information about adverse reactions is codified as **T66**.

Covariables: it is important to control several factors that may interfere with the possibility of a child receives or not the vaccine.

Those variables will be:

Sex: Male or Female.

Age: measured in months and years.

Ethnicity: Caucasian, Asian, Afro-American and others.

Socioeconomical status: according with MEDEA index included into SIDIAP and expressed in percentiles.

DATA COLLECTION

Data will be obtained from SIDIAP (Sistema d'Informació pel Desenvolupament de la Investigació en l'Atenció Primària). That database integrates information from several sources, but mainly from e-CAP, which collects information belonging to Primary Attention, and CMBD (Conjunt Mínim Bàsic de Dades), which contains information from Hospital registers like admission diagnosis, patient's evolution, complications, reasons of discharge, etc. However, there are other information sources into SIDIAP database.

Those data represent nearly an 80% of population in Catalunya.

Through SIDIAP we can access to demographical information such as sex, age, race, socioeconomical status, etc; as well as information about health problems, results of complementary tests and therapeutically procedures or vaccinations received by the patient.

VARIABLE DESCRIPTION AND STATISTICAL ANALYSIS

UNIVARIANT ANALYSIS

❖ Independent variable: it is a dichotomous qualitative variable. It is registered as: Vaccinated or Unvaccinated and described with percentages.

❖ Dependent variables:

- Number of cases of invasive meningococcal disease: it is a discrete quantitative variable. It is defined by mean and standard deviation if it is normally distributed or by median and quartiles in case of non-normal distribution. It will be expressed a confidence interval of 95%.
- Adverse reactions registered: it is a dichotomous qualitative variable. It is registered as presence of adverse reaction associated with vaccination (Yes or No). It will be described by percentages.

Covariables:

- Sex: it is a dichotomous qualitative variable, described by percentages.
- Age: it is a discrete quantitative variable, defined by mean and standard deviation if it is normally distributed or by median and quartiles in case of non-normal distribution. It will be expressed a confidence interval of 95%.
- Ethnicity: it is a categorical qualitative variable, described by percentages.
- Socioeconomical status: it is a discrete quantitative variable and it will be described by mean and standard deviation if it is normally distributed or by median and quartiles in case of non-normal distribution. It will be expressed a confidence interval of 95%.

BIVARIANT ANALYSIS

To compare the independent variable, which is categorical qualitative, with the main dependent variable, which is discrete quantitative, we will use the Mann-Withney test.

To compare the independent variable with the secondary dependent variable, which are both categorical qualitative we will use the Chi ² test.

To compare qualitative variables between them we will use Chi² test, and to compare quantitative variables between them the Pearson rank or Spearman rank, depending if they are normally distributed or not.

MULTIVARIANT ANALYSIS

It will be used a Cox model adjusted for Propensity Score punctuation, for confounding variables.

ETHICAL AND LEGAL CONSIDERATIONS

The present protocol will be presented for its approval to the Comité d'Ètica i Investigació Clínica (CEIC) de l'Institut d'Investigació i Recerca en Atenció Primària Jordi Gol.

Moreover, we will present that protocol to the Agencia Española del Medicamento y Producto Sanitario (AEMPS) since this is a post-authorisation observational study and it has to be classified.

Once we have obtained the Ethics Commitee's approval and the AEMPS's classification, we present the protocol to the Departament de Salut de Catalunya- Subdirecció General de Recerca i Innovació en Salut, since we are using a vaccine which is a drug.

Finally, in a voluntary way, we will register that protocol to the European Network of Centres for Pharmacoepidemiology and Pharmacovigilance (ENCePP) in order to avoid a possible publication bias.

The project will guarantee that the following considerations and legislations are respected:

- World Medical Association -Declaration of Helsinki: Ethical Principles for Medical Reasearch Involving Human Subjects from 1964.
- ❖ Spanish Law: "Ley 14/2007 de Investigación Biomédica"
- Real Decreto 1090/2015- Regulación de los Ensayos Clínicos con medicamentos, Comités de Ética de Investigación con medicamentos y el Registro Español de Estudios Clínicos.
- Orden SAS/3470 de 2009- Directrices sobre Estudios Post- Autorización de Tipo Observacional para Medicamentos de Uso Humano.

Because we are using a preexisting database as SIDIAP where all information is anonymised and codified it is no necessary ask for Informed Consent, according with current legislation:

- Ley Orgánica 41 de 2002- Autonomia del Paciente y de Derechos y Obligaciones en Materia de Información y Documentación Clínica.
- Ley Orgánica 15 de 1999- Protección de Datos de Carácter Personal.

The investigators have no conflict of interests.

STRENGTHS AND LIMITATIONS

As any other study, certain limitations exist. Those limitations can be related with the study design, its associated biases and with the sample's obtention.

STUDY DESIGN

Although Clinical Trial is the best design for assess the effectiveness of a preventive measure, that design would entail several difficulties, which would seriously affect the results obtained and its validity.

The main reason to not perform a Clinical Trial is that given the low incidence of IMD at current moment, it would be necessary to enrol a lot of participants in the study and also a long follow-up period to obtain IMD cases and see if the vaccine is effective or not in its prevention.

Therefore, to carry out a Clinical Trial a big inversion of time and resources will be needed, so it would not be feasible right now.

To solve all that issues it has been choosen a cohort study and a data source as SIDIAP. That data source allows the obtention of sufficient participants, and the design allows its follow-up during an adequate period of time, making feasible the study even the current epidemiological situation.

BIASES

Observational studies have an important limitation, because we cannot randomly assign participants to one group or another.

That fact causes that differences observed may be due to the existence of confounding variables.

For that reason, in this study it is very important controlling that confounding variables. Hence, they are collected during data collection phase and controlled with a multivariant anlysis.

The analysis we will perform will be adjusted with the Propensity Score (PS).

PS is a useful tool that helps to know if we are comparing two groups that are similar between them except for the independent variable we are studying.

So, we establish *a priori* which variables can be confounding and, according with PS punctuation, we will know if two groups are homogeneus and the results that we are observing are due to the measure we are assessing.

SAMPLE

The big sample size required to carry out the study could be a limitation, however because we obtain information through SIDIAP database, which includes a high part of population in Catalunya, we can easily access to all information required as well as obtain a sufficient number of participants in the study.

In fact, using a big sample provides a high external validity to the results since the sample we are studying is highly representative from target population.

WORK PLAN

In this section we are going to describe the phases of the study as well as which activities will include, who is going to carry out every phase and how long is going to take each one.

The study will last 7 years and 4 months and it will be structured in 4 phases.

PHASE 1- Coordination & Development of the protocol (6 months)

- ❖ Activity 1: Meeting to define who is going to participate in the investigation and assigning functions to every member of the research team. All members participate.
 (M1)
- ❖ Activity 2: Defining an Hypothesis, Objectives and Variables for its collection from SIDIAP database. All members participate. (M1-M2)
- ❖ Activity 3: Bibliography research. Three members of the research team. (M1- M2)
- ❖ Activity 4: Pilot test of data extraction, problems detection and correction. Two members of the research team. (M3)
- ❖ Activity 5: Elaboration of final protocol. All members participate. (M3-M4)
- Activity 6: Sending the protocol to the Ethics Committee and to AEMPS for its aproval and classification. Main investigator & another member of the research team. (M4-M6)
- ❖ Activity 7: Register the protocol into ENCePP. Main investigator. (M6)
- ❖ Activity 8: Design a database for the study. One member of the research team. (M3-M6)

PHASE 2- Participants recruitment & Data collection (6 years)

- ❖ Activity 9: Participants recruitment will last 1 year. (M6-M18)
- ❖ Activity 10: Follow- up for every subject included in the study for 5 years. (M6-M78)
- ❖ Activity 11: Data collection. Information regarding variables and covariables for the study will be collected and introduced in our study database. Information will be depurated and reviewed before being introduced into our database. All members participate. (M6-M78)

PHASE 3- Statistical analysis & interpretation of the results (5 months)

- ❖ Activity 12: Data obtained will be analyzed by statistician. One member of the research team. (M78-M80)
- ❖ Activity 13: Investigators will discuss the results obtained, after their statistical analysis. All members participate. (M80-M82)

PHASE 4- Final report elaboration & Publication of the results (5 months)

- ❖ Activity 14: Final report writting. Main investigator. (M83-M85)
- ❖ Activity 15: Final report dissemination: Submitt the results to the principal medical journals to be published. Main investigator. (M85-M87)

STUDY CHRONOGRAM

		2017	2018		2019	2020	2021	2022	2023	2024
PHASE 1- Coordination & l	Devel	opment of	the protocol							'
Act 1- Coordination meeting										
Act 2- Hypothesis, Objectives & Variables										
Act 3- Bibliography research										
Act 4- Pilot test										
Act 5- Final protocol elaboration										
Act 6- Protocol approval										
Act 7- Protocol register										
Act 8- Database design										
PHASE 2- Participants rec	ruitm	ent & Data	collection				'			
Act 9- Participants recruitment										
Act 10 – Follow- up										
Act 11 – Data Collection										
PHASE 3- Statistical analys	sis & i	nterpretat	ion of the res	ults						
Act 12- Statistical analysis										
Act 13- Discussion										
PHASE 4- Final report elab	orati	on & Public	cation of the	results						
Act 14- Final report elaboration										
Act 15- Publication of the results										

BUDGET

This study is observational and certain aspects of daily practice are not modified, such as indications or recommendations for vaccination with Bexsero given by paediatricians and the decision of vaccinate or not vaccinate made by parents, Bexsero's administration place, number of doses, children's visits schedule or Primary or Hospitalary attention in IMD cases (complementary tests performed, treatments administrated).

For that reasons, the cost of Bexsero is not included in the budget. Moreover, paediatricians and nurses who are going to administrate Bexsero and make the visits to the participants, making the recruitment and follow-up will not receive a special compensation.

To make the statistical analysis, a qualified statistician will be hired. He will be payed 25€/hour with an estimated time for this work of 120 hours, so the total amount will be 3.000€.

To create a specific database for our project, a data manager will be hired. Create our own database is an important point, because into SIDIAP there is a lot of information that is not necessary to answer our study question, so data must be debugged and transformed in order to be analysed. In addition, it is necessary to guarantee that data are correctly anonymised in order to not infringe ethical principles. The cost of create the database, extract data from SIDIAP and introduce it into our database, debugger it, encrypt it and maintaining the database for 7 years is estimated of $4.300 \, \text{€/}$ year, so the total amount will be $30.100 \, \text{€.}$

To discuss the results obtained at the end of the study, the meeting will have an estimated cost of $400 \in$.

Publication of the results in Open Access will suppose a cost of 1.500 €.

To summarise the estimated cost of the project, the following box has been made.

PERSONNEL COSTS			
Statistician	25 €/hour x 120 hours		3.000 €
Data manager	4.300 € / year x 7 years		30.100 €
Estimated cost of create our own			
database, import information			
from SIDIAP, debugger data,			
encrypt it and maintaining the			
database for 7 years.			
		SUBTOTAL	33.100 €
MEETING COSTS			
Meeting for results discussion			400 €
		SUBTOTAL	400 €
PUBLICATION COSTS			
Publication of the results in Open A	ccess		1.500€
		SUBTOTAL	1.500 €
	T(OTAL AMOUNT:	35.000 €

FEASIBILITY

With an accumulate incidence rate of 16 cases /100.000 hab per year (14) and a source of data as big as SIDIAP obtaining data from Catalunya and not just from one province, one year should be enough to achieve the sample required or even more participants.

According with the information needed, no modifications have to be done in the e-CAP or CMBD to obtain data about variables, so with current tools it is perfectly possible to start with this study.

In conclusion, all necessary means are available and time periods to achieve the objectives of the study are affordable, so the present protocol is feasible right now.

IMPACT TO THE NATIONAL HEALTH SYSTEM

This study will have a big impact on our National Health System for several reasons.

First, the use of Bexsero is a current topic in discussion since this vaccine is relatively new and it exist a high controversy among paediatricians about if it has to be massively administrated or not. Moreover, there are no strong evidences to support for or against opinions regarding its use.

Therefore, it is important to know if Bexsero is really effective for prevent a severe, life threatening disease which also causes major sequelae in children as the invasive meningococcal disease. In fact, if Bexsero was effective it could be included into the regularly vaccination schedule in order to benefit the entire population.

On the contrary, if the vaccine is not useful for IMD prevention it would be convenient know it in order to avoid using it in healthy children.

Hence, regardless if the hypothesis of the study is true or not the results of the study could change the daily practice in Paediatrics.

Secondary, if our results point that there is an association among being vaccinated with Bexsero and have more adverse reactions, that fact would change current recommendations about that vaccine. Even more, knowing if this association exists could be very useful in order to start other research projects about this topic and stablish a possible causal relationship.

[figure not shown]
BIBLIOGRAPHY

- 2. Ministerio de Sanidad. Guía de Práctica Clínica sobre el Manejo de la Enfermedad Meningocócica Invasiva. Madrid: Ministerio de Sanidad, Servicios Sociales e Igualdad; 2013.
- 3. Gil Á, Barranco D, Batalla J, Bayas JM, Campins M, Gorrotxategi Gorrotxategi P, et al. Prevención de la enfermedad meningocócica por el serogrupo B mediante una vacuna de cuatro componentes. An Pediatr. 2014;16(62):259.e1-259.e23.
- 5. Alonso Salas M, de Carlos Vicente JC, Gil Antón J, Pinto Fuentes I, Quintilla Martinez J, Sánchez Díaz J. Documento de consenso SECIP-SEUP sobre manejo de sepsis grave y Shock séptico en pediatría [Internet]. Sociedad Española de Cuidados Intensivos Pediátricos (SECIP); 2009 [cited 2016 Nov 15]. p. 76. Available from: http://www.seup.org/pdf_public/pub/consenso_sepsis_shock.pdf

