- ❖ The most affected population groups are: children under 5 years old (2.18 cases/100.000 hab) and especially children less than 1 year (8 cases/100.000 hab) followed by teenagers among 15 19 years old (Annex 2).
- ❖ Highest mortality rates are observed among adult population.
- ❖ Carriers rate is highly variable ranging from 8%-10%. Highest rates are observed in teenagers, where it arrives till 25%.

D. Moreno *et al* ⁽¹⁵⁾ show in their work that Spain has an incidence rate of IMD due to serogroup B superior than European average. In fact, it is the fifth country with highest incidence rates of the European Union. By absolute number of cases, Spain is the third country behind United Kingdom and France.

Data about epidemiology of IMD in Europe are graphically represented in **Annex 3**.

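### Five years from enrolment is justified as the high-incidence period, but with entry at any age from 3 months to 5 years about half of that time falls after the fifth birthday and very little in infancy

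*Protocol*

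**What the plan says.** - Entry (Study population, inclusion criteria): "Children aged among 3 months and 5 years old".
- Who enters (Sample protocol, Sample selection): "All children that accomplish previously mentioned criteria will be included". So the entry ages are those of the eligible SIDIAP population, and the protocol does not describe them.
- Enrolment (same section): "The enrolment period starts on June 2017 and finishes on June 2018, lasting 1 year".
- Follow-up and its reason (same section): "The desired follow- up for each participant should be 5 years, because this is the period where higher incidence rates occur".
- Work plan, Activity 10: "Follow- up for every subject included in the study for 5 years. (M6-M78". That is 72 months, or 12 of enrolment plus 60 of follow-up.
- Main objective: "effectiveness of Bexsero in prevention of invasive meningococcal disease in children aged among 3 months and 5 years old".
- Background, Epidemiology: 2.18 per 100,000 for children under 5, and "especially children less than 1 year (8 cases/100.000 hab" per the same source.
- Sample size: 14,108 vaccinated and 70,540 unvaccinated children, 70% efficacy, 16 per 100,000 per year in the unvaccinated, 5% dropout.
- Multivariant analysis: a Cox model adjusted for a propensity score. Age in months and years is a listed covariable.

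**The concern.** The rationale treats five years from enrolment as if it were the first five years of life. The two coincide only for children who enter in early infancy; a child enrolled at 4 is followed to 9. Nothing in the protocol ends follow-up at the fifth birthday.

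Two things are at stake. First, any expected number of cases that carries an under-5 rate through the whole of follow-up will be too high, because much of the person-time is at ages where the protocol's own account puts the risk lower. Second, a single effectiveness figure would pool ages inside and outside the range in the main objective, in proportions set by whoever happens to be enrolled.

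**Working it through.** **1. The plan's own figure.** With k = 5 unvaccinated per vaccinated child, the arcsine formula is n1 = (z_α + z_β)²(1 + 1/k) / (2·asin√p0 − 2·asin√p1)². Taking p0 = 5 × 16 = 80 per 100,000, p1 = 0.30 × p0, two-sided α 0.05 and 90% power gives 19,253 vaccinated (20,267 with 5% dropout). A one-year risk gives 96,304. Neither is 14,108. The nearest 5-year result is 14,382, at 80% power without dropout. The protocol does not state the risk period, and its N does not reproduce. That is a separate matter, and nothing below depends on it.

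**2. Where the person-time falls.** For entry age a (up to 5) and 5 years of follow-up, time after the fifth birthday is a, and time before the first birthday is max(0, 1 − a).

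Uniform entry on 0.25–5 years (assumption):
- after the fifth birthday: mean a = (0.25 + 5)/2 = 2.625 years, 52.5%
- infancy: (0.75²/2)/4.75 = 0.059 years, 1.2%
- ages 1–4: 5 − 2.625 − 0.059 = 2.316 years, 46.3%

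Other entry mixes:

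| Entry mix | After 5th birthday | Infancy |
|---|---|---|
| Uniform, plus one year of new 3-month-olds during enrolment | (4.75×2.625 + 0.25)/5.75 = 2.212 y, 44.2% | (0.281 + 0.75)/5.75 = 0.179 y, 3.6% |
| Upper limit read as the sixth birthday | 60.8% | 1.0% |
| Infants over-represented twofold | 47.1% | 2.0% |
| Infants over-represented fivefold | 37.0% | 3.6% |
| Every child enters at exactly 3 months | 5% | 15% |

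Only the last row supports the rationale, and it conflicts with including all eligible children up to 5 years.

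**3. Rate at ages 1–4.** Reading 8 and 2.18 as annual rates, and with birth cohorts of equal size (assumption): (5 × 2.18 − 8)/4 = 0.725 per 100,000, about one eleventh of the infant rate.

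**4. Expected unvaccinated cases in 70,540 children, before dropout.** The rate from age 5, r, is not given. I take 0.1 to 0.725 per 100,000; for reference, the Epidemiology section gives 0.53 for all ages.
- Flat 2.18 for 5 years: 70,540 × 5 × 2.18/100,000 = 7.7.
- Uniform entry: risk = 0.059×8 + 2.316×0.725 + 2.625×r = 2.42 (r = 0.1) to 4.06 (r = 0.725) per 100,000, or 1.7 to 2.9 cases.
- With new 3-month-olds: 0.179×8 + 2.609×0.725 + 2.212×r = 3.55 to 4.93 per 100,000, or 2.5 to 3.5 cases.

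Age structure alone therefore lowers the expected cases by a factor of about 2.2 (7.7/3.5) to 4.5 (7.7/1.7). Among 14,108 vaccinated children at a rate ratio of 0.30, the same risks give 0.1 to 0.2 cases.

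**5. The same mechanism at the plan's own rate (illustration).** If 16 per 100,000 held at every age under 5 and the rate were zero afterwards, uniform entry gives a risk of 16 × 2.375 = 38 per 100,000 instead of 80. The arcsine n1 at 90% power rises from 19,253 to 40,544. Power at the stated N less 5% falls from about 77% to about 46%.

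**6. Share of cases after the fifth birthday.** Uniform entry: 0.26/2.42 = 11% to 1.90/4.06 = 47%. With new 3-month-olds: 0.22/3.55 = 6% to 1.60/4.93 = 33%. Cases before the fifth birthday would number about 1.5 (2.15 × 0.7054) or 2.3 (3.33 × 0.7054) in the unvaccinated.

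**The case against.** **The age range may mean age at entry.** A cohort defined by entry age with a fixed follow-up is an ordinary design, and the Justification lists duration of protection as unknown, so time after age 5 is informative. This stands. It is why later follow-up should be kept, and why making under-5 person-time the sole primary estimate would be a trade-off and not a correction. It does not rescue the stated reason, which concerns incidence and not duration.

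**The shares rest on an assumed entry mix.** True, but the range in the table is wide and none of its realistic rows supports the rationale.

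**The fall in cases might be laid to the wrong cause.** The plan's inputs, if carried over 5 years, give 70,540 × 80/100,000 = 56 cases. The drop from 56 to 7.7 comes wholly from the conflict between 16 and 2.18 per 100,000 and is not counted here.

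Two stronger readings are tempting, and the documents do not support them:
- A reader might infer that small age imbalances between the cohorts could outweigh the vaccine effect. Under uniform entry, infancy carries 0.47/4.06 to 0.47/2.42 of the risk (12–20%), so removing all infant time from one cohort gives a spurious rate ratio of 0.80–0.88. With new 3-month-olds it carries 1.43/4.93 to 1.43/3.55 (29–40%), giving 0.60–0.71. Both are far from the planned 0.30, and losing all infant time is not a small imbalance.
- A reader might infer that the Cox model is fixed on time since enrolment. The protocol names no time scale, and that choice may be made in an analysis plan.

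**Conclusion.** The point holds as a mismatch between the stated rationale and the design. Follow-up runs from enrolment, while the higher incidence is defined by age. About half of person-time falls after the fifth birthday (52.5% under uniform entry, 44% with new 3-month-olds, 37–61% across the mixes examined) and about 1–4% in infancy. Expected unvaccinated cases fall from 7.7 to about 1.7–3.5.

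The case counts rest on four assumptions: the entry-age mix, equal birth cohorts, a rate of 0.1–0.725 per 100,000 from age 5, and reading the Epidemiology rates as annual. The mismatch itself rests only on the protocol's text. It does not show that the effectiveness estimate would be biased, nor that following children past age 5 is wrong.

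**What to change.** - Correct the rationale. If 5 years from enrolment is wanted for other reasons, such as duration of protection, say so. State whether the age range in the objective means age at entry or attained age.
- Tabulate entry ages in SIDIAP, recompute expected cases by attained-age band (under 1, 1–4, 5 and over) with a sourced rate for each, and restate the power.
- Specify attained age in months as the Cox time scale with delayed entry at enrolment, or stratify by age band.
- Report effectiveness separately for person-time before and after the fifth birthday, so that the result for the age range of the objective can be read on its own.

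**Cost.** A little more analysis and a less favourable stated power. No new data collection is needed: age in months is already a covariable, and attained age is entry age plus follow-up time. The under-5 estimate would omit about 11–47% of cases under uniform entry (6–33% with new 3-month-olds) and rest on very few events. Later follow-up should therefore be kept and reported beside it.
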